7. DATA COLLECTION AND MEASUREMENTS

Outcomes and Measures are collected at baseline, 6, 12, 15 and 18 months at mental health programs. Table 2 shows these measures.

Primary Outcome: The primary outcome will be 7-day point prevalence smoking abstinence at 18 months, defined as self-report of 7 days of not smoking, confirmed by expired CO <8ppm with a Bedfont Smokerlyzer II.^{175,181,182} Biochemical verification with available urine cotinine (if not on NRT) and/or anabasine will be used as needed to confirm self-reported abstinence, particularly if the validity of CO is expected to be low (e.g. COPD or difficulty forming an adequate seal on the smokerlyzer); and if CO is greater than 8 as this could be from second hand smoke or smoked cannabis.¹⁴⁸⁻¹⁵⁰

7-day smoking abstinence at 6, 12 and 15 mo. are secondary outcomes.

Other Secondary outcomes focus on AHA metrics for health risk behaviors¹⁶⁵ and include: a) continuous abstinence with 1) % continually abstinent over 3mo. (based on self-reports of abstinence since last visit, using timeline follow-back)¹⁸³, and biochemical verification at 15 and 18 month visits), 2) total days abstinent in the study with the same method; b) Weight and BMI; c) Physical fitness with 6-minute walk;¹⁸⁴⁻¹⁸⁶ and d) Healthy diet.¹⁸⁷ We will assess 10-year probability of a CVD event with the global Framingham Risk Score (FRS) incorporating smoking, total and HDL-cholesterol, systolic blood pressure and diabetes mellitus.¹⁸⁸ Others include: health status (SF-12)¹⁸⁹; Quality of life (Euroqol);¹⁹⁰⁻¹⁹² psychiatric symptoms (BPRS);¹⁹³ ED use and hospitalizations.

We will also examine the difference of mean CO change over time between intervention arms, and, among

Protocol: Trial of Integrated Smoking Cessation, Exercise and Weight Management in SMI

continuing cigarette smokers, change of mean number of cigarettes smoked per day over time between intervention arms.

Measurement methods: Measures for all participants are detailed below, and will be conducted using standardized procedures, and following quality control procedures as in ACHIEVE and Drs. [name]' trials.^{51,61,121,125} The data collection team will be certified in and experienced with measures, and monitored by the study coordinator. All measures are collected at baseline, 6, and 18 months. At 12 months and 15 months we collect contact information, medications, smoking information, weight and event surveillance.

Demographics, Medical History: We will collect demographics, contact information, medical history with checklist of conditions, Rose Angina Questionnaire, and assess alcohol use with the AUDIT (Alcohol Use Disorders Identification Test) and questions from the Semi-Structured Assessment for the Genetics of Alcoholism (SSAGA-II) and substance use with ASI-Lite.^{151,152}

Psychiatric diagnoses and medications are abstracted from charts. Participants confirm medications.

Tobacco smoking will be assessed with questions regarding self-reported smoking behavior since the last data collection visit and 6-item Fagerstrom Test of Nicotine Dependence (FTND).¹⁴⁷ At baseline we also assess smoking history including age of onset, cigarettes/day, pack-years, number of prior quit attempts, reasons for treatment failure or relapse, and self-efficacy around quitting. **We will measure** expired carbon monoxide (CO) and will also obtain urinary cotinine and anabasine as appropriate to confirm smoking status.^{148,150,153}

Weight will be measured to the nearest 0.1 lb by a high quality digital scale with participants wearing light indoor clothes without shoes. Weight will be measured in lbs. for ease of interpretation by participants and converted to kg for calculation of BMI, calculated as the Quetelet index.

Height to the nearest 0.1 cm will be measured at baseline using a wall-mounted stadiometer.

Physical fitness will be measured by the 6-minute walk test, a valid predictor of VO₂ max and responsive to increases in regular moderate physical activity.¹⁵⁴⁻¹⁵⁶

Blood pressure will be determined by the OMRON 907 XL, a validated device that records BP using an oscillometric technique.¹⁵⁷ On 3 visits, 1 week apart, 3 measurements (each separated by 30 seconds) will be obtained on the right arm of participants after they rest quietly in the seated position for at least 5 minutes.¹⁵⁸

Fasting blood measures will be collected, centrifuged, aliquoted and sent for processing. Total and HDL cholesterol, triglycerides, glucose, LDL cholesterol will be estimated by Friedwald equation unless direct measurement is needed.¹⁵⁹ An aliquot will be frozen for future investigation of putative CVD risk markers. Urinary protein will be measured.

Waist circumference will be measured with anthropometric tape, in a plane 1 cm above the navel.

Questionnaires will be used for a variety of purposes including baseline descriptive data, outcomes to assess intervention effects, and mediators to assess potential causal pathways. Instruments may be added or removed depending on scientific and logistic considerations including participant burden.

Planned instruments are described here:

Healthy diet. Block Fat, Fruit, Vegetable and Fiber Screener Questionnaires provide self-report of daily fruit, vegetable intake, and percent energy from fat.¹⁶⁰ A sugar-sweetened beverage instrument will be used.¹⁶¹ Health status will be measured by the Medical Outcomes Study SF-12.¹⁶²

Protocol: Trial of Integrated Smoking Cessation, Exercise and Weight Management in SMI

Quality of life will be assessed with the Euroqol EQ-5D, a brief 6-item instrument that is valid in persons with schizophrenia and bipolar disorder that can be used for cost-effectiveness analyses.¹⁶³⁻¹⁶⁵ We will use the Neighborhood Questionnaire to assess participants' home environments for safe places to exercise and places to purchase healthy food, a questionnaire on food and shopping habits, and the Pittsburgh Sleep Quality Index.¹⁶⁶⁻¹⁶⁸

Medication adherence will be measured with an adapted questionnaire based on the Morisky Medication Adherence Scale for each class of medications for CVD risk factors (e.g., antihypertensives, lipid lowering medications).¹⁶⁹

Psychiatric symptoms will be assessed by the Brief Psychiatric Rating Scale (BPRS).^{170,171} Interviewers will receive training on administration and scoring and will rate 5 sample video administrations of the BPRS to ≥85% to gold standard ratings by consensus raters.

Self-reported physical activity will be measured with the Godin Leisure Time Exercise Questionnaire.¹⁷²

Social Support will be assessed with the Medical Outcomes Study Social Support Questionnaire.^{173,174}

To assess social networks around smoking, we will use the personal network approach measurement (also called the 'egocentric' approach) to elucidate the network ties that surround a focal individual.¹⁷⁵⁻¹⁷⁹ In particular, we will ask each participant to identify the wide range of network members with whom individuals interact and measure the participant's understanding of the connections among those people. We will assess health literacy with the Health Literacy Skills Instrument. The sexual behaviors of persons with serious mental illness have implications for their emotional and physical well-being. These behaviors also affect the need for health care services that are focused on sexually transmitted diseases, family planning, and childbearing. Reproductive health will be measured with NHANES survey questions.¹⁸⁰ Health care access will be measured using adapted specific Behavioral Risk Factor Surveillance System Questions.¹⁸¹ Access to technology will be measured using adapted questions based on PEW Research Center.¹⁸²

Table 2. Data Collection Measures for All Participants	BL	6	12	15	18
Contact information	X	X	X	X	X
Demographics	X	X			X
Medical conditions	X	X			X
Substance Abuse	X	X	X	X	X
Medical history	X				X
Rose Angina	X				
Psychiatric diagnoses	X				
Medications	X	X	X	X	X
Physical measures					
Blood pressure	X	X			X
Weight	X	X	X	X	X
Height	X				
Waist circumference	X	X			X
6 minute fitness walk	X	X			X
Fasting blood measures	X				X
Urinary Cotinine and anabasine	X	X	X	X	X
Urinary Protein	X				X
Smokerlyzer CO	X	X	X	X	X
Instruments					
Healthy diet	X	X			X
Tobacco measures	X	X	X	X	X
Health status	X	X			X
Quality of Life	X	X			X
Neighborhood Questionnaire	X				X
Sleep habits	X				X
Medication Adherence	X	X	X	X	X
Psychiatric Symptoms	X	X			X
Physical Activity	X	X			X
Social Support					
Healthcare access questions	X				X
Technology	X				X
Reproductive health	X				X
Social Networks	X				X
Health Literacy	X				
Event Surveillance-safety	X	X	X	X	X

Event surveillance. We will identically apply a process to each randomized group and collect self-reported symptoms, health care utilization and records related to CVD and mental health outcomes, including ED use and hospitalizations, and use the SAFTEE¹⁸³ for possible medication side effects.

Intervention Measures: In active intervention participants, to measure interim progress towards goals, inform case management and analyze potential mediators: we will track 1) attendance at integrated groups, individual visits, exercise classes (staff report) and gym use (sign-in records), 2) self-reported smoking since last visit expired CO, 3) study medication use by self-report/interim pill counts, 4) weights from weigh-ins and text responses, and 5) texting use (% completed responses, smoking and eating behavior, weight, daily steps).

Interviews: We will use a purposive sample of active intervention participants, and we will conduct interviews after the 18-month intervention to gain an understanding of participant perceptions of and satisfaction with the program.

Organizational factors (Substudy of factors related to intervention implementation): To better understand factors influencing implementation of the intervention and potential future dissemination, we will conduct semi-structured interviews with selected community mental health program leadership and staff, psychiatrists and health coaches with involvement in the intervention, and targeted (N=50), and we also will survey more widely mental health staff and clinicians at mental health programs (N=150). Interviews will ask about the intervention's perceived effectiveness, ease, associated barriers, fit within the organization and financial models for continued support. We will discuss issues around physician prescribing of smoking cessation pharmacotherapy. We will interview before the intervention and then at end of study to assess changes due to the intervention. Surveys will focus on assessing implementation climate and attitudes towards evidenced-based practices, perceptions of the role of various sectors of the health care and social services system in addressing clients' somatic health needs; perceptions of the TRIUMPH intervention, its usefulness; barriers to implementation; stigma toward persons with SMI; and patient communication. We will gain an understanding of factors impacting intervention acceptability, feasibility and future sustainment, and prepare groundwork for dissemination. Study team members will conduct interviews in person and administer surveys using Qualtrics or paper.

Elements of RE-AIM framework:¹⁸⁴ We will collect data to report as many aspects of the trial as possible. For Reach, we will estimate the number of smokers and compare those eligible to those signing screening consent. We will also compare characteristics of those screened to those enrolled. For Efficacy /Effectiveness, we will report all our outcomes including potential adverse events. For Adoption, we will track pharmacotherapy prescription/use, attendance in all intervention contacts and use of text messaging, and report any site differences. For Implementation, we will track delivery of all intervention components, analyze cost (B3i5), and incorporate information from interviews about facilitators and barriers. For Maintenance, from interviews, we will explore plans for sustainment. We conceptualize this study as a Hybrid Type I trial testing a clinical intervention while gathering information on its delivery and its potential for future implementation.¹⁸⁵

8. QUALITY ASSURANCE AND QUALITY CONTROL

Quality Assurance pertains to activities that promote collection of high quality data, and Quality Control refers to activities that detect emerging data issues with sufficient time to implement appropriate corrective actions. Our approach to Quality Assurance includes: 1) preparing a manual of operations; 2) implementing a master trainer model to train and certify other staff; 3) train and certify all data collectors; 4) recertify data collectors at least annually; 5) routinely calibrate equipment; 6) maintain logs of certified staff and calibrated equipment. Our approach to Quality Control includes: 1) monitoring counts of completed data collection items; 2) monitoring distribution of trial outcomes, overall, by data collector and site; 3) record lag time in data entry; 4) issue queries on missing data, out of range values or illogical data relations; 4) review types and distribution of data entry errors; and 5) prepare reports for staff, investigators and NIMH and DSMB on Quality Control.

9. RANDOMIZATION AND BLINDING

Randomization to intervention or control will be stratified by site and by whether participants are ready to set a quit date within 30 days or within 6 months. We aim to enroll approximately 60% of the participants in the strata for being ready to quit in 30 days. To prevent predictability of assignment, the randomization schedule will be created in variable block sizes. Prior to randomization, the study coordinator will confirm the participant meets all eligibility criteria and required baseline data are collected. Due to the nature of the intervention, participants and coaches will be aware of group assignment, however, we will take considerable efforts to ensure data collection staff will be kept blinded to assignment (e.g., exclude them from all parts of intervention delivery, remind participants not to share group assignment, designate/track unmasked staff).

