Pharmacotherapy for smoking cessation in SMI is universally recommended, but infrequently used in most settings.^{12,72} The study physician(s) are trained education on use, risks, benefits and monitoring of pharmacotherapeutic cessation aids in SMI, and will prescribe and monitor medications for intervention participants, coordinating with and supported by others on the study team. These psychiatrists will discuss medication choice with participants and take their preferences into account while assessing clinical appropriateness for varenicline+/-NRT, and bupropion+NRT (patches with lozenges/gum) Varenicline has been associated with higher abstinence,^{67,203,204} so we expect it will be used preferentially. We will use standard dosing for varenicline and bupropion. Varenicline dosing is 0.5mg for 3 days, 0.5 mg bid for 4 days and then 1mg bid. Subsequent prescriptions are 1mg po bid. Varenicline will be provided by Pfizer. Bupropion is 150mg pod bid SR formulation. Those with adverse effects with varenicline limiting tolerability will be offered a lower dose, or bupropion+NRT. Bupropion+NRT will be offered to those with varenicline contraindications, and vice versa. Once initiated, the goal will be for participants to use medication for the study duration for sustained abstinence, however, if needed they may stop and then resume medication or switch therapies. This flexible approach should improve cessation rates. Physician study visits for smoking cessation pharmacotherapy are separate from the participants' regular mental health visits. Participants will continue to see their regular psychiatrist for mental health care. The physicians prescribing smoking cessation pharmacotherapy will be study team members and will communicate with the participants' regular psychiatrists about the intervention, but will not deliver regular mental health care.

Exercise program. Three approaches will enable participants to achieve 150 mins/week of moderate intensity

Protocol: Trial of Integrated Smoking Cessation, Exercise and Weight Management in SMI

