All study staff will complete the web-based Collaborative Institutional Training Initiative (CITI) for Basic Human Subjects Research, Conflict of Interest Training and training in the Health Insurance Portability and Accountability Act (HIPAA).

Study participants will be 220 adults, aged 18 and older with nicotine dependence who attend psychiatric day programs or outpatient mental health clinics affiliated with Johns Hopkins Bayview or Family Services Agency, Inc. All participants in the trial provide written informed consent using procedures reviewed and approved by Johns Hopkins Institutional Review Boards. There are separate consents for the screening and intervention phases of the study. The consent forms cover all procedures done as part of screening and the intervention.

Sources of materials

Sources of materials: Data collectors will conduct assessments in-person; their regular presence on-site during data collection periods will minimize participant burden and allow measures to be performed according to participants' schedules and availability. Eligibility will be determined through in-person screening at the study sites. To determine eligibility for the study, we will obtain permission from potential subjects to talk with mental health program staff and clinicians and contact their primary care physician and psychiatrist concerning any medical or psychiatric reasons for study exclusion. We will communicate with these physicians to ensure there are no contraindications to participating in the intervention.²²⁹ We will document assessments and in each subject's study chart. We will also communicate this information to participants and ask participants for permission to communicate this information to their medical and psychiatric providers.

Safety Monitoring

Participant safety will be closely monitored. Protection of research participants begins with the eligibility criteria, which are designed to exclude individuals with a serious medical condition or psychiatric instability that would make it unsafe for them to take part in the smoking cessation, weight maintenance and exercise intervention. During the study, regular mental health and primary care will be provided by the participant's usual mental health and primary care providers, not by the study. Participants will be made aware of this delineation of responsibility.

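### Data collectors are to stay blinded, but nothing separates the medication and side-effect questions from the BPRS and smoking interview, and discretionary verification of abstinence has no fixed rule or masked adjudicator

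*Combined protocol and SAP*

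**What the plan says.** Section 9 accepts that participants and coaches know the assignment. Of the outcome staff it says "we will take considerable efforts to ensure data collection staff will be kept blinded to assignment", with three examples of how: "exclude them from all parts of intervention delivery, remind participants not to share group assignment, designate/track unmasked staff". Section 14 adds that data collectors cannot open intervention data in the database.

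Section 7 sets the visit content: "All measures are collected at baseline, 6, and 18 months", and "At 12 months and 15 months we collect contact information, medications, smoking information, weight and event surveillance". Table 2 marks medications, tobacco measures, CO, urine cotinine and anabasine, and event surveillance at baseline and at 6, 12, 15 and 18 months. It marks psychiatric symptoms at baseline, 6 and 18 months. On the source of the list: "Psychiatric diagnoses and medications are abstracted from charts. Participants confirm medications". Event surveillance uses the SAFTEE for medication side effects in both arms.

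On who does this, Section 7 describes a certified data collection team for these measures, and Section 15 (Sources of materials) says "Data collectors will conduct assessments in-person". The BPRS is an interviewer rating: "Interviewers will receive training on administration and scoring".

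Section 10 has study physicians prescribe varenicline with or without NRT, or bupropion with NRT, to intervention participants. Once started, "the goal will be for participants to use medication for the study duration for sustained abstinence". Controls receive usual care, a quit-line referral and printed material (Section 11).

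The primary outcome (Sections 7 and 13) is a 7-day self-report confirmed by CO below 8 ppm. Urine cotinine, for those not on NRT, and/or anabasine may be brought in as needed, including where CO is thought unreliable or is above 8.

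**The concern.** In a trial open to participants and coaches, the blinded collector is the only masking that the protocol describes. The medication list and the side-effect inquiry are part of the collector's own visit, and they carry information about the arm that reminders and database permissions do not block.

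Two outcomes are exposed. The first is the BPRS, which is rated by judgement and compared between arms by linear mixed model. It is also the measure of psychiatric symptoms in a population for whom Section 16 discusses psychiatric events reported with varenicline and depressive symptoms after quitting. A rater who suspects the arm could shade the rating either way. The second is the primary outcome. CO gives it an objective component, but its discretionary urine step depends on NRT status, which tracks arm. That step can turn a CO failure into an abstainer.

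**Working it through.** The plan gives no figure on this point, so there is none to reproduce. The check compares passages and adds two short calculations.

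**1. Do the stated safeguards reach this route?**

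| Safeguard | Reaches the medication and side-effect questions? |
|---|---|
| Collectors kept out of intervention delivery (Section 9) | No; the list is a data collection item |
| Participants asked not to share their assignment (Section 9) | No; naming a drug is not naming an arm, and the form asks for it |
| Unmasked staff designated and tracked (Section 9) | Partly; it could log a collector who has learned the arm, but no consequence for later ratings is stated |
| No access to intervention data (Section 14) | No; the participant confirms the drug in person |

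No section sets the order of items within a visit or assigns medications to a separate person.

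**2. Which visits?** Medications are listed at four follow-ups: 6, 12, 15 and 18 months. Table 2 puts event surveillance at the same four; the monitoring plan in Section 17 speaks of 6-month intervals for symptom inquiry, which still includes 6 and 18 months. The BPRS has two follow-ups, 6 and 18 months. A collector could therefore learn the arm before the 18-month BPRS at any of three earlier visits (6, 12, 15).

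**3. How informative is the list?** Let u be the share of active participants, and c the share of controls, with a cessation drug listed. The documents give neither, so both are assumptions. With 1:1 allocation and a guess of active whenever a drug is listed:

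- share of correct guesses = 0.5u + 0.5(1 − c)
- chance that a participant with a listed drug is active = u/(u + c)

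| u | c | Correct guesses | Active, given drug listed |
|---|---|---|---|
| 0.90 | 0.02 | 0.45 + 0.49 = 0.94 | 0.90/0.92 = 0.98 |
| 0.70 | 0.05 | 0.35 + 0.475 = 0.825 | 0.70/0.75 = 0.93 |
| 0.50 | 0.20 | 0.25 + 0.40 = 0.65 | 0.50/0.70 = 0.71 |
| 0.30 | 0.20 | 0.15 + 0.40 = 0.55 | 0.30/0.50 = 0.60 |

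The first three rows span the main range, 65-94%. The last row shows that low active use with high control use brings the guess close to chance.

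**4. How much can discretion move the primary outcome?** With 220 randomised equally, each arm has 110, so one reclassified participant changes that arm's abstinence rate by 1/110 = 0.9 percentage points. At the control rates assumed in Section 13 (3-5%), expected control abstainers number 0.03 × 110 = 3.3 to 0.05 × 110 = 5.5. A few decisions would therefore be visible in the result. The documents do not say how many participants would need the urine step.

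**The case against.** The strongest reply is that the documents are silent here rather than contradictory. A reader might infer that the blinded rater must personally record the medication list. No passage says so: Section 7 describes the abstraction and confirmation of medications without naming a role, and nothing says the list comes before the BPRS. The Section 9 measures are examples, and form order would normally sit in the manual of operations that Section 8 mentions. This stands as a limit on the claim. It does not remove the gap, because Sections 7 and 15 give the assessments to the data collection team and name nobody else for this item.

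A reader might also infer that the list reveals the arm outright. It does not. Section 16 describes bupropion as an antidepressant and requires an antidepressant for participants with major depression, so it can appear in either arm. NRT is sold over the counter, and Section 13 allows that controls may obtain drugs elsewhere. Active participants may stop, resume or switch. The 40-50% enrolled as not ready to quit within 30 days (Section 9 implies 40%, Section 13 50%) may start drugs early but need not. Against this, Section 10 calls cessation drugs infrequently used in most settings, which argues for low background use in controls.

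Third, there are other protections. BPRS interviewers train to at least 85% against gold-standard ratings, and outcome distributions are monitored by collector (Section 8). Training does not stop a drift related to arm, and monitoring by collector would not show one unless it were also split by arm.

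Finally, Table 2 schedules urine for everyone, so the documents do not support a reading in which the collector chooses whom to test (although the Section 7 text says as appropriate). The discretion lies in how results are used, and no passage gives that decision to collectors. It gives it to nobody, and that is the remaining problem.

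**Conclusion.** The point holds as a gap in the masking arrangements, with a low-cost remedy. The medication list and side-effect inquiry are an uncovered route by which a collector can often infer the arm, and nothing keeps that collector from the BPRS or the smoking self-report. Independently, use of urine results in the primary outcome is discretionary, depends on NRT status, and has neither a fixed rule nor a masked adjudicator.

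The 65-94% figure rests wholly on assumed use of 50-90% in the active arm and 2-20% in control, and falls to 55% at 30% and 20%. The size or direction of any BPRS shift cannot be derived from the documents. They do not show that the assessors were unblinded, that the BPRS comparison is biased, or that the primary outcome is compromised. The BPRS is the more exposed outcome; the primary outcome is partly protected by CO.

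**What to change.** 1. **Visit order.** At each visit, complete and lock the BPRS, the smoking self-report and timeline, and CO before any medication or side-effect question. Order protects only the current visit. Where existing staffing allows, a different collector should therefore rate a participant's later BPRS once one has learned the arm. Section 9 does not say that unmasked staff attend data collection visits, so their availability should not be assumed.

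2. **Abstinence classification.** Write a fixed rule that derives abstinence from self-report, CO, cotinine and anabasine, covering unreliable CO, readings above 8, and a reading of exactly 8, which the present wording leaves unassigned. Have someone masked to arm apply it, with NRT status supplied as a data field. Because NRT status hints at the arm, the rule should leave no room for judgement. State whether the same urine step applies in the CO below 6 ppm sensitivity analysis.

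3. **Check on masking.** Record the collector's guess of arm at 18 months and report it by arm.

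The cost is a less flexible visit order, some rescheduling of collectors and a little more analysis work; no new measure is needed.

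The version 1.2 notes (May 2020) record that 24-month data were not obtained, so visits may already be complete. In that case items 1 and 3 are no longer available. Item 2 can still be done before analysis, and the report can say who collected medications and whether they also rated the BPRS.
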